2.2. Rationale for Proposed Study

In the proposed feasibility study of six subjects, we plan to evaluate the safety and efficacy of CT/DBS in patient subjects who have recovered from a moderate or severe brain injury (initial GCS 12 or lower) to an outcome level ranging from GOSE 5 to the lower half of GOSE 7. As briefly outlined below and based on our pre-clinical studies of CT/DBS in intact non-human primates and rodents with and without TBI, and our clinical experience with CT/DBS in MCS/EMCS subjects, we outline the rationale that this new patient TBI population is optimally matched to obtain clinically meaningful benefits from CT/DBS (see [Figure 1](#)). We are targeting a collection of well-defined neuronal populations within the central thalamus that have known anatomical and physiological specializations that both provide a key role in arousal regulation during cognitively-mediated behaviors and are particularly vulnerable to dysfunction in the setting of multi-focal, non-selective brain injuries.

As per [Figure 1](#), an optimal benefit of CT/DBS in patients recovering from moderate to severe traumatic brain injury is proposed for the functional outcomes captured across the GOSE level 5 to 7 range on this scale. The conceptual basis for targeting this population includes evidence that CT/DBS can have a significant behavioral facilitation effect across the range of minimally conscious state ([name] et al. 2007) to executive function in the intact mammalian forebrain (Baker et al. 2011, 2012, 2013). Patients with initial moderate to severe brain injury (GCS<12) and recovery to GOSE level 5 to lower 7 are anticipated to demonstrate significant cerebral deafferentation leading to a large population of neocortical, striatal and thalamic neurons that do not reach their full potential dynamic range as a result of deafferentation but could under conditions of sufficiently increased background synaptic activity.

Figure 1: Effects of CT/DBS are Present across the Continuum from MCS to Healthy Intact Brain

2.3. Rationale for CT/DBS

The fundamental rationale for CT/DBS as a therapeutic modality in the SMTBI patient population with recoveries in the range of GOSE 5-7 targeted here is based on several considerations:

- the frequent observation of a specific clustering of neuropsychological impairments in this patient population
- the specific role of frontostriatal systems in establishing these specific neuropsychological functions in the brain
- the functional role of the central thalamus in supporting frontostriatal systems and regulating activity across frontostriatal neuronal populations in response to cognitive demands
- the common pathology of deafferentation of the central thalamus arising across all moderate to severe brain injuries with a maximal predicted preservation of neuronal cell types in the GOSE 5-7 level recovery from STBI patient population
- clinical and pre-clinical studies demonstrating that CT-DBS can facilitate behaviors in humans and rodents with TBI, and that these specific neuropsychological functions affected in the SMTBI patient population can be significantly facilitated by CT-DBS in a human subject with very severe brain injury, as well as in intact non-human primates.

2.5. Role of frontostriatal systems in supporting sustained attention, working memory and processing speed

Human neuroimaging and studies in non-human primate provide a convergence of evidence that frontostriatal systems organize and support the neurophysiological substrate underpinning a group of psychological capacities collectively described as executive functions (Stuss and Knight 2013 [30]). At the core of this wide-ranging set of capacities are the neuropsychological functions of sustaining attention; holding instructions or briefly presented information in memory; and processing information quickly ahead of executing a variety of motor responses such as gestures and spoken language. Persistent activity in specialized neuronal populations in frontal cortex, striatum and thalamus has been consistently identified as supporting sustained attention, working memory, and processing speed (McCormick et al. 2003 [18]). The loss of dynamic range of activation of frontostriatal systems in response to demands on executive function systems can thus be understood as the result of deafferentation of these neurons resulting from brain injuries and of their main source of activation in the central thalamus (see below). The dominance of psychological effects of STBI by the cluster of impaired sustained attention, working memory, and cognitive processing speed deficits is the direct result of the

graded impact in those patients remaining functionally affected by their injuries of the loss of this general purpose base function of frontostriatal systems (Duncan and Owen 2003 [7]).

2.6. Role of central thalamus in pathophysiology of moderate to severe TBI

The central thalamus is anatomically specialized to provide strong synaptic drive across the frontal and prefrontal cortices and rostral striatum in response to cognitive demands (reviewed in [name] 2008 [23]; Mair and Hembrook 2012 [16]). Control of the activation of central thalamus in response to these demands emanates from medial frontal cortex and is modulated by the full set of brainstem ‘arousal system’ inputs from cholinergic, noradrenergic, and other monoamine pathways. Diffuse axonal injury results in widespread disconnection across the cerebrum with secondary neuronal death of these central thalamic neurons arising as a common pathology; the concentration of damage in the central thalamus (intralaminar) and related association nuclei indexes the severity of outcome (Maxwell et al. 2006 [17]). These nuclei show a greater vulnerability to multifocal brain injury because of their widespread projections that lead to their disproportionate deafferentation that is associated with diffuse injuries. Loss of input from these neurons secondary to this deafferentation leads to a failure to maintain sufficient membrane depolarization to produce or sustain action potential firing rates typical of frontocortical and striatal neuronal populations in the wakeful state; in studies of severely brain injured human subjects who remain within the very severely impaired categories of minimally conscious state and confusional state this effect can be measured in differences in regional cerebral metabolic rates (Fridman et al. 2014 [9]); the level of recovery of central thalamic metabolism in these studies grades level of recovered behavioral function. Several circuit- level specializations of the central thalamus underlie dysfunction of the forebrain after STBI and deafferentation of the central thalamus ([name] 2010 [25]).

3. Study Objectives

This is a feasibility study to inform the safety and efficacy of central thalamic-deep brain stimulation (CT-DBS) in the treatment of chronic cognitive impairment and residual disability caused by traumatic brain injury (TBI).

4. Study Design

This is a single arm, sponsor-investigator feasibility study to be conducted at a single investigational site.

5. Study Device

This study utilizes the Medtronic Percept PC Deep Brain Stimulation system. The Percept PC has been approved by the FDA for Bilateral stimulation of the internal globus pallidus (GPi) or the subthalamic nucleus (STN) as an adjunctive therapy in reducing some of the symptoms of advanced, levodopa-responsive Parkinson's disease that are not adequately controlled with medication. The device is being provided by the manufacturer, Medtronic, and no changes have been made to the device for use in this study.

The Percept PC system consists of the neurostimulator, leads, extensions and clinician and patient programmers. As shown in [Figure 2](#) below, there are separate programmers for the clinician and the patient.

Figure 2: Percept PC System

6. STUDY PLAN

The research plan is organized around the central aim of acquiring pilot clinical data that will inform the safety and efficacy of central thalamic-deep brain stimulation (CT-DBS) in the treatment of chronic cognitive impairment and residual disability caused by TBI. We intend to recruit 6 adults with a history of moderate to severe TBI (GCS = 3-12) who continue to demonstrate neuropsychological impairment and functional disability at least 24 months post-injury (Glasgow Outcome Scale- Extended = 5-7) {Wilson, 1998, Structured interviews for the Glasgow Outcome Scale and the extended Glasgow Outcome Scale: guidelines for their use}.

Following study enrollment, participants will be randomly assigned to 1 of 3 baseline conditions lasting 30, 44, or 58 days. Two participants will be assigned per condition. The staggered baseline schedule will enable assessment of CT-DBS effects within individual subjects and across subject pairs. Each participant will also be randomly assigned to a treatment withdrawal or continuation condition. This process is explained in detail in [Section 6.3](#) of this document.

Following a 30 to 60-day presurgical baseline phase to ensure surgical readiness and establish current level of function across multiple domains, participants will undergo implantation of a deep brain stimulator in the central lateral nucleus of the thalamus. Implantation of the stimulator will be followed by a staggered post-surgical baseline that will increase progressively for each pair of participants. After a 14-day stimulation titration phase, CT-DBS will be

administered for 90 consecutive days. Following the unblinded stimulation phase, participants will enter a 21-day double-blinded treatment withdrawal phase. The study will formally conclude at the end of the withdrawal phase. Participants will be given the option to continue to use the device following study termination, if they are receiving benefit.

The study design includes 3 unique features that were incorporated to detect treatment effects, reduce sources of bias and estimate generalizability:

- Subject pairs will be randomized to one of 3 progressively-increasing baseline observation periods. Should treatment be effective, improvements in performance on the outcome measures will occur in temporal contiguity to the onset of CT-DBS. This design element will help differentiate the effects of CT-DBS from random fluctuations in function.
- Treatment will be withdrawn in a double-blinded manner- neither the investigators nor the subjects will have knowledge of when CT-DBS is discontinued. This feature will minimize the influence of examiner and subject bias on the outcomes of interest.
- Outcome assessment across multiple subjects following establishment of a stable baseline will enable identification of a significant treatment effect and permit inferences to be drawn concerning generalizability of results ([name], 2007 [22], Behavioral improvements with thalamic stimulation after severe traumatic brain injury).

Study Operations: This is a single site study. All procedures, assessments and follow-up care will be take place at Stanford University under the leadership of [name]. The study co-investigators from Weill-Cornell, Spaulding Rehabilitation/Harvard, Cleveland Clinic and University of Utah will travel to Stanford for procedures. Two additional Weill-Cornell faculty members will travel to Stanford to do EEG testing and other data collection. [name] at Weill-Cornell will lead the data analysis.

The members of the team have had successful remote collaborations for over a decade. The project has adequate funding for remote collaboration tools for conference calling and document sharing, travel for in-person meetings and a project manager.

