1. SYNOPSIS

Table 1: Protocol Synopsis

Title	Central Thalamic Deep Brain Stimulation for the Treatment of Traumatic Brain Injury
Study Groups	Single arm study of 6 subjects
Study Objective	Pilot study to inform the safety and efficacy of central thalamic-deep brain stimulation (CT-DBS) in the treatment of chronic cognitive impairment and residual disability caused by traumatic brain injury (TBI).
Study Device	Medtronic Percept PC system for central thalamic deep brain stimulation (CT-DBS)
Clinical Hypothesis	CT-DBS will be safe in the study population and will enhance cognitive function as indexed by the primary outcome measure
Study Population	Adult patients with a history of moderate to severe TBI (GCS ≤ 12) who continue to demonstrate neuropsychological impairment and functional disability (Glasgow Outcome Scale- Extended = 5-7) at least 24 months post-injury. The 6 participants will be separated into three pairs.
Study Design	Single arm, open-label, sponsor-investigator study
Number of Sites	1 site
Total Number of Subjects	18 subjects screened with a total of 6 subjects enrolled for randomization and implantation
Duration of Study	The total duration of the study is 12 to 14 months depending on cohort.
Inclusion Criteria	
 • History of moderate to severe TBI based on worst GCS score within first 48 hours of injury (acceptable GCS range = 3-12) • Age 22-60 • At least 24 months from date of onset • Fluent in English and able to independently provide consent • Retains decision-making capacity and is able to function independently (i.e., unsupervised) in the home setting • Multiple unsuccessful attempts to sustain competitive employment or complete an academic degree-granting program of study • Either receives no CNS stimulants or other medications known to affect cognitive function, or on stable doses of these medications for the last three months (see additional information regarding concomitant medications below)

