attention, working memory and complex visual pattern recognition. We postulate based on our prior investigation that the effects of CT-DBS are mediated by activation of downregulated frontocentral cortical regions and will produce improvements in processing speed and executive functions as measured by standardized neuropsychometric measures (Trails B, continuous performance tasks) and customized behavioral tasks assaying sustained attention and working memory. We also anticipate that these changes in cognitive efficiency will facilitate improvements in vocational productivity, psychological health and self-reported quality of life.

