6.3. Randomization to Multiple Baseline Condition and Treatment Withdrawal

Following study enrollment, participants will be randomly assigned to 1 of 3 baseline conditions lasting 30, 44, or 58 days. Two participants will be assigned per condition. The staggered baseline schedule will enable assessment of CT-DBS effects within individual subjects and across subject pairs. Each participant will also be randomly assigned to a treatment withdrawal or continuation condition. Neither the investigator nor the participant will have knowledge or be apprised as to whether DBS is on or off during this period. For participants assigned to the treatment withdrawal condition, DBS will be switched off for 21 days (on days 170, 184, and 198 for cohorts 1-3, respectively) immediately after completing the 90-day unblinded treatment phase. Participants randomized to the continuation condition will continue to receive stimulation 12 hours per day over the same 21-day period. Upon conclusion of the 21-day treatment withdrawal phase, participants will undergo a final re-assessment on the multi-dimensional outcome assessment battery and on the electrophysiologic measures (on day 191, 205, or 219, depending on cohort). Currently there are no known safety issues related to withdrawing stimulation. The purpose of this follow-up visit is to determine if there is evidence of loss of effect in those assigned to the treatment withdrawal condition, and to evaluate the influence of

intervening factors on the effectiveness of DBS. The trial will be considered complete at the end of the treatment withdrawal phase.

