6.5. Screening and Preoperative Baseline Evaluation

One to two months before DBS implant surgery (with 1 month defined as 30 days \pm 3 days), participants will complete physical and neurological screening examinations and complete laboratory studies to ensure study eligibility and suitability for surgery. A screen failure is defined as a potential participant who has been consented for screening but is not enrolled for randomization and implantation. A screen failure does not meet all inclusion criteria and/or has answered or tested affirmatively to any exclusion criteria. A potential participant may also fail screening if they are deemed unsuitable for participation based on the clinical judgment of the sponsor investigator. We estimate the screen failure rate to be 3:1, which is based on efficiently pre-screening interested participants, and extensive team review of each case prior to screening.

Participants will also undergo pre-operative multi-dimensional baseline assessment using a battery of cognitive (e.g., attention, memory, information processing speed, executive functions), psychological health (e.g., depression, anxiety) functional status (e.g., employment level) and quality of life (e.g., satisfaction with life) measures (see *Description of Outcome Assessments* below). A structured interview will also be conducted to obtain additional background information and determine pre-injury levels of academic, vocational and social function. These evaluations can be done either on a single day or on multiple days.

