(Holloway et al. 2005 [12]). A high-resolution volumetric CT scan will be obtained and these images will be imported into the surgical planning station and fused with the previously obtained MRI images, and the final target location determined. On the day of surgery, the patient will be positioned in a custom head cradle. The patient's anatomy will be registered to the neuronavigational system by touching each fiducial marker with a passive planar registration probe equipped with reflective spheres, which can be tracked by the cameras of the surgical navigation unit. Entry points will be marked on the scalp and the patient will be prepared and draped in a sterile fashion. After burr-hole placement, high-impact plastic towers will be attached to the skull bilaterally with 3 titanium bone screws. A sterile reference arc will be fastened to the base of the platform to allow real-time tracking for maximum accuracy. Each fiducial marker will be touched through the drape to perform registration again. Alignment of the trajectory will be accomplished by adjusting the frameless device platform to orient the trajectory to the planned target, using the guidance view of the target provided by the planning software.

Implantation will be guided either by intraoperative imaging (O-arm or MRI) or by microelectrode recording and intraoperative macrostimulation via the DBS leads. Image-guided procedures will be performed under general anesthesia. Microelectrode-guided procedures will be performed under conscious sedation, titrated according to the judgement of the anesthesiology team. In either case, routine procedures for DBS placement will be used. In a recent meta-analysis, no significant difference was found between the two techniques with regard to targeting accuracy and symptom reduction (Ho et al. *Mov Disord* 2017). Based on the results from the first 5 patients in this study, there does not appear to be a unique neurophysiological signal associated with the CL nucleus. In addition, intraoperative stimulation has not caused side effects that proved informative with relation to the eventual postoperative lead location. Therefore, the final patient in the study will be implanted using image guidance, which we believe will result in equivalent or improved accuracy.

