6.7. Post-Surgical Washout Phase

Participants will enter the washout phase following hospital discharge. The length of the baseline will be staggered for each participant pair. The purpose of this phase is twofold: (1) to provide a 30-day surgical washout for resolution of any transient physiological or behavioral effects of surgery and (2) to detect the temporal onset of the stimulation effects for each subject, should these occur at the time of stimulation titration onset. At the end of the surgical washout period, the multidimensional outcome assessment battery that was administered during the pre-surgical baseline phase will be repeated to assess for any changes in function before CT-DBS is switched on (see *Description of Outcome Assessments* below). A CT scan will be performed on day 65 to assess the final lead location, after any post-surgical changes have been allowed to resolve.

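### For the Trail Making test, the staggered baseline can neither date nor isolate a stimulation effect, and Section 11 does not use the randomised withdrawal comparison

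*Combined protocol and SAP*

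**What the plan says.** The efficacy hypothesis in the Synopsis is that CT-DBS "will enhance cognitive function as indexed by the primary outcome measure", and Section 11 names that measure as the Trail Making test.

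Three statements describe what the design can show:
- Section 6, on the 30/44/58-day stagger: "Should treatment be effective, improvements in performance on the outcome measures will occur in temporal contiguity to the onset of CT-DBS". It adds that the stagger helps tell the treatment effect from random fluctuation.
- Section 6, on assessment across participants: "following establishment of a stable baseline will enable identification of a significant treatment effect".
- Section 6.7 gives as a purpose of the post-surgical phase "to detect the temporal onset of the stimulation effects for each subject", should effects begin when titration starts.

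The section text places the outcome battery as follows:
- Test 1, before surgery (Section 6.5): "Participants will also undergo pre-operative multi-dimensional baseline assessment using a battery of cognitive" and other measures.
- Test 2, at the end of surgical washout, before switch-on (Section 6.7).
- Test 3, at the end of the 90-day unblinded phase (Section 6.9).
- Test 4, after the 21-day withdrawal or continuation phase (Section 6.3). Its purpose is "to determine if there is evidence of loss of effect in those assigned to the treatment withdrawal condition".
- Section 6.11 adds an assessment of neuropsychological status at six months, without naming tests.

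Section 11 provides descriptive summaries and unspecified exploratory analyses, and notes the small sample. It mentions neither the stagger nor the withdrawal randomisation.

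**The concern.** A multiple-baseline design earns its inference from repeated measurement. Some participants are observed on treatment while others, at the same time, are still observed at baseline, and each series is dense enough to show when it shifts. One test at each end of a long window gives neither.

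As the plan stands, a faster Trail Making time at 90 days could be read as an onset-linked effect of CT-DBS, when practice, passage of time and recovery from surgery would produce the same data. This has consequences, because Section 6.10 expects judgements of individual benefit to draw on evidence that DBS caused the neuropsychological change. The comparison that could support a controlled statement has no place in the statistical plan. This point concerns inference only and suggests no rule for continuing stimulation.

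**Working it through.** **Inputs.** Switch-on day 66/80/94 and 14 days of titration (Section 6.8). Treatment of 90 days (Section 6.9). Switch-off day 170/184/198 and final assessment day 191/205/219 (Section 6.3). Six participants, two per cohort. Test error is taken as independent with SD 1.

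**1. The plan's own schedule.** 66 + 14 + 90 = 170, 80 + 104 = 184 and 94 + 104 = 198. Adding 21 gives 191, 205 and 219. All agree with Section 6.3. The last day of the 90-day phase is therefore 169/183/197.

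**2. Window that contains any change.** If test 2 is on the day before switch-on (65/79/93): 169 − 65 = 183 − 79 = 197 − 93 = 104 days. If test 2 is on day 65 for everyone: 104, 118 and 132 days. Counting test 3 on the switch-off day adds one day. A change at any time in the window gives the same data. The stagger steps are 14 days.

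**3. Overlap between cohorts.** Cohorts differ in stimulation state only on days 66 to 93, and no on-stimulation Trail Making test falls there. The latest pre-stimulation test (day 93) precedes the earliest on-stimulation test (about day 169) by 169 − 93 = 76 days, or 169 − 65 = 104 if test 2 is on day 65 for all.

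**4. Separability over tests 1 to 3** (18 observations).
- *Participant plus test-number effects:* 6 + 2 = 8 parameters, rank 8. The stimulation column equals the test-3 indicator, so the rank stays at 8 and stimulation is not estimable.
- *Participant, surgery step, linear drift and stimulation:* rank 9 of 9. Without the stagger this model is not estimable, so drift comes only from cohort differences in day. With a common pre-operative test day (assumed), Var(drift) = 1.5/784, where 1.5 = 1 + 1/2 and 784 = 4 × 14². With W the mean window, SE² = 2/6 + W² × 1.5/784.
  - W = 104: SE = √(0.333 + 20.694) = 4.59. The 95% half-width is 2.262 × 4.586 = 10.4 SD (9 df).
  - W = 118 (test 2 on day 65 for all): SE = √(0.333 + 26.640) = 5.19, half-width 11.7 SD.
- *Dropping the surgery step:* SE 1.16 (1.42 with test 2 on day 65 for all) if the pre-operative test is assumed on day 1, and 1.30 (1.67) if on day 15. That precision comes mostly from the slope between tests 1 and 2, and so assumes surgery does not alter it.
- *Plain pre-post change, for reference:* SE = √(2/6) = 0.58.

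**5. Stable baseline.** There are two pre-stimulation tests, with surgery between them. Their difference mixes practice, time and surgery.

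**6. Nominal significance.** A signed-rank test on six pre-post changes can reach two-sided p = 2/64 = 0.031.

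**7. Withdrawal comparison** (change from test 3 to test 4, by group). Half-width = t(0.975, 4 df) × √(1/a + 1/b) = 2.776 × √(1/a + 1/b), in SD of change. The allocation ratio is not stated, so these splits are assumptions:

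| Split | Half-width |
|---|---|
| 3 v 3 | 2.27 |
| 2 v 4 | 2.40 |
| 1 v 5 | 3.04 |

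**The case against.** **The schedule is inferred.** The available text has no visit table, and the plan implies visits beyond the four batteries. For example, Section 6.9 samples electrophysiology on day 139/153/167, which is day 59 of the 90-day phase (139 − 80). None of these visits is tied to the Trail Making test. Tables run from 1 to 2 without a gap, and the only appendix in the contents is the programming SOP. The reservation stands to this extent: a schedule with repeated Trail Making tests within phases would answer the onset part.

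**The claims are not specific to the Trail Making test.** Section 6 speaks of the outcome measures generally, and Section 6.7 is conditional. Titration observations (Appendix 1) and the interleaved on/off EEG and Attention Network Test blocks (Section 7.7.1) lie nearer to stimulation changes. This is fair, and it is why the point is confined to the primary outcome. Those blocks are exploratory, acute and not described as randomised.

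**The precision figure depends on the model.** This also stands. A reader might take the ratio of 4.6 or 5.2 to 0.58 (8 to 9 times) as a property of the design, but step 4 shows it rests on a surgery step plus linear drift over tests 1 to 3. With test 4 added, an assumed 3 v 3 split and a fully reversible effect, the SE is √[(1 + 1/3)(1/3 + 1/3)] = 0.94 even with test-number effects, and 0.65 with a surgery step plus drift. The 0.94 comes wholly from the withdrawal randomisation, which supports the fix.

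**This is a feasibility study that admits limited analysis.** The caveat in Section 11 is about sample size. More participants on the same schedule would leave stimulation confounded with test order.

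**Conclusion.** The point holds for the Trail Making test and should be fixed. Any change can be placed only within about 104 days (up to 132 on the day-65 reading), against a 14-day stagger, and no cohort is tested on stimulation within 76 days of another cohort's last baseline test. The onset and random-fluctuation statements in Sections 6 and 6.7 describe a property the design lacks for this outcome, and a stable baseline cannot be established. The conclusion rests on the schedule as the section text gives it, so confidence is moderate. It does not rest on the 4.6 SD figure.

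Two stronger readings are not supported:
- *That no significant result is possible.* A pre-post p of 0.031 is attainable. What is missing is attribution to stimulation.
- *That the withdrawal comparison is undefined.* Section 6.3 gives its conditions, blinding, days, battery and purpose. The gap is that Section 11 does not take it up as an analysis.

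Which part of the test is primary, and which day is the reference, are clarifications that carry no weight here.

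**What to change.** **(a) Sections 6 and 6.7.** Limit the temporal-contiguity, random-fluctuation, stable-baseline and onset-detection statements with text such as:

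> For the Trail Making test the staggered baseline is not used to date onset of effect. The change to the end of the 90-day phase is reported as an uncontrolled pre-post change, open to practice and surgical effects.

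If a schedule with repeated Trail Making tests within phases exists, state it instead.

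**(b) Section 11.** Add as the controlled estimate:

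> Change in Trail Making time from the end of the 90-day phase to the end of the 21-day phase, by randomised withdrawal or continuation group, with individual values, numbers per group, difference in means and 95% CI. Precision is very limited; a CI that includes zero is not evidence of no loss of effect.

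Label this post hoc if outcome data from that phase have already been seen. Section 6.6.1 shows the study is well advanced ("Based on the results from the first 5 patients in this study"), although that passage concerns surgical findings and does not show that Trail Making data were examined.

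**Clarification only.** Name the Trail Making part and the reference test day in each cohort.

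**Cost.** Wording and reporting only, with no new visit, test or participant. The efficacy language becomes less favourable, and the randomised interval will be wide and may look null.
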